#### 2.1.1 General Definitions

#### **Study Treatment**

The term study treatment/treatment group will refer both to Deferasirox FCT (DFX) or Phlebotomy.

#### Date of First/Last Administration of Study Treatment

For Deferasirox FCT:

- The date of first administration of study treatment is derived as the first date when a non-zero actual dose of study treatment was administered as recorded on Dose Administration Record (ZQ) Electronic Case Report Form (eCRF).
- The date of last administration of study treatment is defined as the last date when a nonzero actual dose of study treatment was administered as recorded on ZQ eCRF.

For Phlebotomy:

- The date of first administration of study treatment is derived as the first date when a non-zero volume of blood removed was recorded on Phlebotomy Record eCRF (FAZU) on or after the randomization date.
- The date of last administration of study treatment is defined as the last date when a nonzero volume removed of blood was recorded on Phlebotomy Record eCRF (FAZU). This date will also be referred as 'last date of study treatment'.

#### **Study Day**

The study day **for safety assessments** (e.g. adverse event onset, laboratory abnormality occurrence, vital sign measurement, Electrocardiogram (ECG), Ocular, etc.) will be calculated using the start date of study treatment as the reference. For assessments occurring

- On or after the start date of study treatment, the study day will be calculated as (date of safety assessment) (start date of study treatment) + 1. Study day 1 will therefore be the first day of study treatment.
- **Before the start date of study treatment**, the study day will be calculated as (date of safety assessment) (start date of study treatment).

For example, if an adverse event starts 3 days before the start of study treatment the study day displayed on the listing will be negative, i.e. -3.

The study day **for efficacy assessments** (i.e. serum ferritin) will be calculated using the randomization date as the reference. For assessments occurring

- On or after randomization date, the study day will be calculated as (date of non-safety assessment) (date of randomization) + 1. Then study day 1 will be the day of randomization.
- **Before randomization date**, the study day will be calculated as (date of non-safety assessment) (date of randomization).

The study day will be displayed in the data listings.

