7.1.4 Treatment period

The study treatment duration is 24 months (104 weeks). Patient visits will occur bi-weekly for the first 4 weeks, then every 4 weeks from Week 4 until 104 (EOT).

All visits should be scheduled respective to the randomization date (Day 1), rather than in relation to previous visits.

After completing screening, eligible patients will be enrolled and randomized to receive phlebotomy or deferasirox FCT. For deferasirox FCT, the target daily dose is calculated by the physician based on the patient's actual body weight.

At the start of treatment, patients randomized to deferasirox FCT will receive 7 mg/kg once daily. Patient randomized to phlebotomy may receive treatment at a frequency determined by the treating physician.

For details on study design and dose adjustments, see Section 4 and Section 6.3.

For details on assessments during the treatment period, see Table 7-1.

FRANCE SPECIFIC ONLY: The additional assessments of creatinine and creatinine clearance at Week 1 and Week 3 after start of treatment, and weekly checks of creatinine and creatinine clearance during the first month of dose increases, both specific to patients enrolled

in sites from France only, are NOT included in the Table 7-1, and should be regarded as unscheduled visits.

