#### Baseline

Baseline is considered as the result of an investigation describing the 'true' uninfluenced state of the subject.

For **efficacy evaluations**, (e.g. serum ferritin), the last available assessment before or on the date of randomization is taken as 'baseline' value or 'baseline' assessment.

For **safety evaluations** (e.g. laboratory, vital signs, ocular etc.) the last available assessment before or on the date of start of study treatment is taken as 'baseline' value or 'baseline' assessment.

If subjects have no value as defined above, the baseline result will be missing.

If an assessment is planned to be performed prior to the first administration of study treatment in the protocol and the assessment is performed on the same day as the first administration of study treatment, it will be assumed that it was performed prior to study treatment administration if assessment timepoint is not collected or is missing. Unscheduled assessments will be considered in the determination of baseline.

Subjects who start treatment and discontinue from the study on the same day may have 2 different sets of data collected on study Day 1, one being reported to the Day 1 visit, the other reported to the EOT visit. Data reported at the EOT visit are not eligible for baseline selection.

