#### **On-treatment Period**

The overall observation period (for both Deferasirox and Phlebotomy) will be divided into three mutually exclusive segments:

- Pre-treatment period: from day of subject's first informed consent to the day before first administration of study treatment;
- On-treatment period: from day of first administration of study treatment to 30 days after last administration of study treatment;
- Post-treatment period: starting at day 30+1 after last administration of study treatment to end of study.

Safety summaries (tables, figures) include only data from the on-treatment period with the exception of baseline data which will also be summarized where appropriate (e.g. change from baseline summaries). For additional details refer to specific section – Section 2.6.3 details on AEs and Section 5.3.2 on Ocular assessments.

However, all safety data (including those from the post-treatment period) will be listed and those collected during the pre-treatment and post-treatment period will be flagged.

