# 5.3 Time-Windows

# 5.3.1 Safety Laboratory Assessments

Safety laboratory data (biochemistry, hematology, and urinary parameters as well as serum creatinine, creatinine clearance and proteinuria) will be collected at screening visits, at each regularly subject visit and at end of treatment visit.

Novartis	Confidential	Page 34 of 36
SAP Amendment 1		Study No. CICL670F2203

If two or more assessments are performed within a time window, then the assessment closest to the planned visit is used in analyses by time window. When two values are equidistant from the planned assessment, the later one is used in analyses. When multiple values are reported on the same day then the average value is used in analyses. For parameters with categorical results, the one from central laboratory is used in analyses.

Table 5-3 shows the defined time windows.

Time Window	Planned Visit Timing	Time Window Definition	
On treatment			
Baseline	On or before Study Day 1*	≤ Study Day 1	
Week 2	Study Day* 8	Study Days 2 – 11 (excluded baseline assessment)	
Week 4	Study Day* 22	Study Days 19 – 25	
Every 4 weeks thereafter			
Week $y=4+(4*k)$	Study Day (4+4*k-1)*7+1	Study Days	
(with $k = 1, 2, 3, 4, 5, 6, 7, 8, 9$ ,		(5+4*k-1)*7+1-14 to	
10, 11,,25)		(5+4*k-1)*7+1+13	
End of treatment	NA	Data collected at EOT visit are included if obtained within the next 30 days of last non-0 dose for DFX intake / non 0 volume removed for Phlebotomy	

Table 5-3 Time windows for safety laboratory data

\*Study Day 1 = first day of study treatment

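### Table 5-3 windows count from the first bleed but visits are scheduled from randomisation, so a control patient first bled 15 or more days after randomisation has on-schedule monthly laboratory and vital-sign data put in the wrong week or in none

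*SAP*

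**What the plan says.** **Visit calendar.** Protocol 7.1.4 ties it to randomisation: "All visits should be scheduled respective to the randomization date (Day 1), rather than in relation to previous visits". Deferasirox is dispensed on Day 1 (protocol Table 7-1). For controls, protocol 7.1.4 says "Patient randomized to phlebotomy may receive treatment at a frequency determined by the treating physician", and protocol 6.6.3.3 has the procedure done at a phlebotomy centre or hospital. No section sets or limits the date of the first bleed. SAP 1.1 describes treatment in both arms as beginning on Day 1, which states an intention and not a limit.

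**Analysis clock.** SAP 2.1.1 uses two reference dates. Ferritin days count from randomisation. The study day for safety assessments "will be calculated using the start date of study treatment as the reference". For phlebotomy that start is "the first date when a non-zero volume of blood removed was recorded on Phlebotomy Record eCRF (FAZU) on or after the randomization date". Table 5-3 sets the windows for laboratory data and, through SAP 2.6.8, for vital signs. Its footnote reads "Study Day 1 = first day of study treatment".

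**Related definitions with the same anchor.** For safety data "the last available assessment before or on the date of start of study treatment is taken as 'baseline' value". The first observation period is given as "Pre-treatment period: from day of subject's first informed consent to the day before first administration of study treatment".

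**The concern.** Visits run on one clock and are sorted into weeks by another. In the deferasirox arm the two should nearly coincide. In the phlebotomy arm they differ by the lag from randomisation to the first bleed, which the plan leaves open. A late start moves a control patient's visits to earlier safety days and can carry them across a window boundary.

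The by-visit laboratory and vital-sign summaries and boxplots would then set the arms side by side at different times since randomisation. Some control visits would drop out of those outputs altogether. One blood draw would also carry one study day for ferritin and another for chemistry.

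**Working it through.** **Inputs**
- Visit of Week w: 7w days after randomisation (protocol 7.1 and 7.1.4; a week is 7 days). Counting randomisation as Day 1, this is Day 7w + 1.
- Tolerance: ±3 days at Weeks 2 and 4, ±7 days at monthly visits (protocol 7.1).
- Windows (SAP Table 5-3): Week 2, Days 2–11; Week 4, Days 19–25; Week w = 4 + 4k, from (5 + 4k − 1)×7 + 1 − 14 to the same centre + 13.
- L: days from randomisation to the first bleed. The documents give no value.

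**1. The table's own planned days.** (w − 1)×7 + 1 gives Day 8 for Week 2 and Day 22 for Week 4, as stated. It also gives the ocular days of Table 5-4: 162, 358, 526 and 722.

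**2. Monthly windows.** Since 5 + 4k − 1 = w, the window is Day 7w − 13 to Day 7w + 14. Week 8 is Days 43–70, Week 12 is 71–98, Week 100 is 687–714 and Week 104 is 715–742.

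**3. Visits exactly on schedule.** The safety day is 7w + 1 − L. It lies in its own window when 7w + 1 − L ≥ 7w − 13, that is, L ≤ 14.
- L = 14: Week 8 is Day 43, and 25 of 25 visits from Week 8 to Week 104 fit.
- L = 15: 0 of 25 fit. Week 8 is Day 42 (between the Week 4 and Week 8 windows, so in none), Week 12 is Day 70 (labelled Week 8), and Week 104 is Day 714 (labelled Week 100).

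**4. Visits within ±7 days.** With deviation d from −7 to 7, a visit is misplaced when d < L − 14. Taking the 15 days as equally likely (an assumption):

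| L | Misplaced |
|---|---|
| 7 or less | 0/15 |
| 8 | 1/15 |
| 14 | 7/15 |
| 15 | 8/15 |
| 21 | 14/15 |
| 22 or more | 15/15 |

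**5. Sensitivity to the week convention.** If sites followed the SAP's planned days, (w − 1)×7 + 1, every visit would fall 7 days earlier. The exact-date threshold would then be L = 8 instead of 15.

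**6. Reach.** The ferritin endpoints count from randomisation. Worst-value tables use all on-treatment values regardless of window (SAP 5.2.2), and the liver-threshold counts use worst values. The end-of-treatment row is filled from the EOT visit, so Week 104 data can still appear there. Post-baseline ocular windows are wide: the first exact-date miss is Week 76, Day 533 − L against a lower limit of 442, so L = 92 (526 − L on the planned days, so L = 85).

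**7. Counting from randomisation.** A visit within ±7 days falls on Days 7w − 6 to 7w + 8, always inside 7w − 13 to 7w + 14, whatever L is. Weeks 2 and 4 fall on Days 15 and 29 and fit neither Days 2–11 nor Days 19–25. With ±3 days (12–18 and 26–32) they still miss. That is a separate fault and affects both arms.

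**The case against.** **A long lag is not the plan.** SAP 1.1 has treatment beginning on Day 1, entry ferritin is at least 500 µg/L, and protocol 2.5 describes weekly or biweekly removal while ferritin is above normal. This stands: the number affected is unknown and may be zero. But the SAP's own start-date rule allows any delay.

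**Time since first treatment is a declared scale, the same in both arms.** At L = 15 the Week 12 visit is 69 days after the first bleed, 13 days from 8 weeks (56) and 15 from 12 weeks (84), so Week 8 is arguably the nearer label. This stands in part. It does not rescue the Week 8 visit, which is lost. By Table 5-3's own planned days, Day 70 is 20 days from Week 8 (Day 50) and 8 from Week 12 (Day 78). And the arms are still compared at different times since randomisation.

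**Stronger readings that a reader might infer, and why the documents do not support them**
- *Every permitted visit is misplaced from L = 15.* This is true only of visits exactly on the scheduled day. Within tolerance it takes L = 22.
- *The control baseline is wrong.* An on-schedule Week 2 sample does become the safety baseline at L = 14 or more, and Week 4 at L = 28 or more. But SAP 2.1.1 wants the uninfluenced state, and a pre-bleed value is untreated.
- *The SAP wrongly deletes early control AEs.* Protocol 10.5.1 starts treatment emergence at the first dose or first phlebotomy, and 10.5.3.1 ends the pre-treatment period the day before. The SAP follows both. Such AEs leave the summary tables but stay in the listings with a flag, and 15 days is 15/728, about 2%, of 104 weeks.
- *Ocular follow-up is misassigned.* At these lags the post-baseline ocular windows still hold.

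**Conclusion.** The mismatch is certain from the text; how often it bites is not known. For monthly visits exactly on schedule the break is sharp: all 25 fit at a 14-day lag and none at 15. Within the visit tolerance the misplaced share rises from none at L = 7 to 8/15 at L = 15 and all at L = 22. This rests on Week w meaning 7w days after randomisation and, for the shares, on equally likely visit days. Without a distribution of L, the number of affected controls is anywhere from 0 to the 50 planned.

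The damage is confined to by-visit laboratory and vital-sign summaries and boxplots, which are descriptive. It is worth correcting because the remedy is cheap, but it does not touch the primary endpoint or time to response.

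**What to change.** **Windows.** In SAP 5.3.1, let Table 5-3 count days from randomisation in both arms, as ferritin already does, and change its footnote to match. Correct the Week 2 and Week 4 limits in the same edit so that they contain Days 15 and 29 with their ±3 days. Table 5-4's post-baseline windows need no change for this reason.

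**Keep** the first-treatment definitions of safety baseline and treatment-emergent AEs.

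**Add** a summary of the lag from randomisation to first bleed, and one supplementary control-arm row for AEs, including ocular AEs, that start between the two dates.

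**Cost.** SAP wording, one reference date in the windowing program, one short summary and one table row. There is a small downside. Early control-arm windows may hold values taken before the first bleed, and SAP 2.1.1 limits safety summaries to on-treatment data plus baseline. The SAP should say that such values are flagged, and that a value used as baseline is not also counted as post-baseline. Week labels will then mean time since randomisation, not time since first treatment, and table footnotes should say so.

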# Time Unit

A month length is 30.4375 days (365.25/12). If duration is reported in months, duration in days will be divided by 30.4375.

#### Baseline

Baseline is considered as the result of an investigation describing the 'true' uninfluenced state of the subject.

For **efficacy evaluations**, (e.g. serum ferritin), the last available assessment before or on the date of randomization is taken as 'baseline' value or 'baseline' assessment.

For **safety evaluations** (e.g. laboratory, vital signs, ocular etc.) the last available assessment before or on the date of start of study treatment is taken as 'baseline' value or 'baseline' assessment.

If subjects have no value as defined above, the baseline result will be missing.

If an assessment is planned to be performed prior to the first administration of study treatment in the protocol and the assessment is performed on the same day as the first administration of study treatment, it will be assumed that it was performed prior to study treatment administration if assessment timepoint is not collected or is missing. Unscheduled assessments will be considered in the determination of baseline.

Subjects who start treatment and discontinue from the study on the same day may have 2 different sets of data collected on study Day 1, one being reported to the Day 1 visit, the other reported to the EOT visit. Data reported at the EOT visit are not eligible for baseline selection.

#### **On-treatment Period**

The overall observation period (for both Deferasirox and Phlebotomy) will be divided into three mutually exclusive segments:

- Pre-treatment period: from day of subject's first informed consent to the day before first administration of study treatment;
- On-treatment period: from day of first administration of study treatment to 30 days after last administration of study treatment;
- Post-treatment period: starting at day 30+1 after last administration of study treatment to end of study.

Safety summaries (tables, figures) include only data from the on-treatment period with the exception of baseline data which will also be summarized where appropriate (e.g. change from baseline summaries). For additional details refer to specific section – Section 2.6.3 details on AEs and Section 5.3.2 on Ocular assessments.

However, all safety data (including those from the post-treatment period) will be listed and those collected during the pre-treatment and post-treatment period will be flagged.

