6.1.1 Dosing regimen

Study treatments	Pharmaceutical form and route of administration	Dose	Frequency and/or Regimen
Deferasirox FCT	Tablet for oral use	7 mg/kg (Initial dose)	Daily
Phlebotomy	Venipuncture	NA	determined by PI

Table 6-1 Dose and treatment schedule

After a 4-week screening period, eligible patients will be randomized 2:1 to receive deferasirox FCT or phlebotomy.

Patients randomized to deferasirox FCT will receive 7 mg/kg once daily. The daily dose is calculated based on the patient's weight, then rounded up or down to the nearest whole tablet according to the available strengths of deferasirox FCT tablets (90 mg, 180 mg, and 360 mg; see Appendix 14.1). After 3 months (12 weeks), adjust dose as needed based on SF levels listed below with the maximum dose adjustment of 3.5 mg/kg/day per month.

- SF < $300 \mu g/L$ Decrease to 3.5 mg/kg/day
- SF 300-1000 µg/L Maintain 7 mg/kg/day
- SF > 1000-2000 μ g/L Increase to 10.5 mg/kg/day
- SF > 2000 μ g/L Increase to 14 mg/kg/day

When SF reaches the study target $\leq 100 \ \mu g/L$, deferasirox FCT must be interrupted and the patient enters the maintenance phase.

During the maintenance phase, when SF \geq 300 µg/L, deferasirox FCT 3.5 mg/kg/day may be re-initiated. If deferasirox FCT 3.5 mg/kg/day is not controlling SF and it continues to increase, increase to a maximum 7 mg/kg/day. Treat until the SF reaches \leq 100 µg/L, then interrupt treatment again.

During regular study visits, the investigator or pharmacist will dispense the appropriate number of deferasirox FCT tablets to each patient. The number of tablets of each strength dispensed will be recorded in the study Drug Dosing Log. Each time deferasirox FCT is dispensed, the investigator must provide detailed instructions to patients, instruct them to take the assigned amount of study drug, and return all unused study medication every 4 weeks. Returned study medication must be counted and recorded. The field monitor must note the drug accountability during site visits and at the completion of the trial.

Medication labels must be in the local language and comply with the legal requirements of the countries where the study is implemented. Labels will have study identifier and storage conditions for the study drug, but no patient information.

Patients should swallow the required number of deferasirox FCT, with or without a light meal, and around the same time each day.

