10.5.3 Secondary safety objectives

Secondary safety objectives include:

- Safety and tolerability of deferasirox FCT and phlebotomy over 24 months
- Change from baseline in visual acuity (ETDRS), intra-ocular pressure, retina or/and optic nerve abnormalities, and lens abnormalities at months 6, 12, 18, and 24.
- Safety and tolerability of deferasirox FCT in patients who interrupt due to $SF \le 100 \ \mu g/L$ and re-initiate therapy when > 300 $\mu g/L$.

See Section 3 for details on safety objectives. Descriptive statistics will be provided for all safety objectives using the Safety set.

Safety and tolerability between deferasirox FCT and phlebotomy during 24 months of study period will be assessed through the incidence of new or worsening AEs, abnormal and clinically significant laboratory findings, and other abnormal safety findings. See Section 10.5.3.2, Section 10.5.3.3, and Section 10.5.3.4 for details.

To assess the effect of deferasirox FCT and phlebotomy, the change from baseline in visual acuity (ETDRS), intra-ocular pressure, retina or/and optic nerve abnormalities, and lens abnormalities will be summarized descriptively by treatment and by visit. The detailed analysis will be detailed in the SAP.

Incidence of AEs in patients who interrupted deferasirox FCT at least once due to $SF \le 100 \mu g/L$ and re-initiated $\ge 300 \mu g/L$ will be tabulated and listed. The detailed analysis will be detailed in the SAP.

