10.5.3.1 Analysis set and grouping for the analyses

For all safety analyses, the safety set will be used. All listings and tables will be presented by treatment group.

The overall observation period will be divided into three mutually exclusive segments:

- 1. Pre-treatment period: from the day of a patient's informed consent to the day before the first dose of study medication or first phlebotomy
- 2. On-treatment period: from the day of the first dose of study medication to 30 days after the last dose of study medication or last phlebotomy
- 3. Post-treatment period: starting at day 30+1 after last dose of study medication or last phlebotomy.

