#### 2.6.5 Adverse Events of Special Interest (AESI)

An adverse event of special interest is a grouping of adverse events that are of scientific and medical concern specific to compound ICL670. These groupings are defined in the eCRS using MedDRA terms, SMQs, HGLTs (high level group terms), HLT and PTs. Customized SMQs (NMQ) may also be used. A NMQ is a customized group of search terms which defines a medical concept for which there is no official SMQ available or the available SMQ does not completely fit the need. It may include a combination of single terms and/or an existing SMQ, narrow or broad. The latest version of the eCRS available at the time of the analysis will be used.

For each specified AESI, number and percentage of subjects with at least one event of the AESI occurring during on treatment period will be summarized.

Summaries of these AESIs will be provided for each of the two treatment arms by grouping and preferred term -

- AESIs, regardless of study treatment relationship
- AESIs, with suspected study treatment relationship
- Serious AESIs regardless of study treatment relationship
- Serious AESIs with suspected study treatment relationship
- AESIs leading to study treatment discontinuation
- AESIs requiring dose adjustment or study treatment interruption
- AESIs requiring additional therapy
- AESIs Outcomes Recovered or Recovering
- Deaths (all and on-treatment)

A listing of all grouping levels down to the MedDRA preferred terms used to define each AESI will be generated.

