#### 2.6.7 Laboratory Data

On analyzing laboratory, data from all sources (central and local laboratories) will be combined. The summaries will include all assessments available for the lab parameter collected no later than 30 days after the last study treatment administration date (see Section 2.1.1).

The following summaries will be produced for hematology, urinary, and biochemistry laboratory data (by laboratory parameter and treatment):

- Descriptive Statistics for lab results and change by from baseline time point and treatment arm
- Shift tables using notable/extended ranges to compare baseline to the worst on-treatment value for key lab parameters (see Table 2-1)
- Shift tables using the low/normal/high/(low and high) classification to compare baseline to the worst on-treatment value.
- Trends of key lab parameter values over time (baseline and selected on-treatment timepoints) will be displayed via boxplots based on time windows and corresponding tables displaying the statistics used for the box plots by the selected time points.

The following listings will be produced for the laboratory data:

- Listings of all laboratory data, with classification relative to the laboratory normal range.
- Listing of all lab abnormalities based on notable/extended ranges

Parameter	Criteria
Absolute neutrophils	$< 1.5 \times 10^{9}$ /L (extended range $< 0.5 \times 10^{9}$ /L)
Platelets	$< 100 \times 10^{9}$ /L (extended range $< 50 \times 10^{9}$ /L)
Hemoglobin	< 100 g/L
ALT and AST	$> 5 \times$ ULN and $> 2 \times$ baseline (extended range $> 10 \times$ ULN and $> 2 \times$ baseline)
Total bilirubin	> 2 x ULN
Serum creatinine	> 33% increase from baseline and > ULN at 2 consecutive measurements at least 7 days apart
Creatinine clearance	< 60 mL/min at 2 consecutive measurements at least 7 days apart (extended range < 40 mL/min at least 7 days apart)
Urinary protein/creatinine ratio*	$\geq$ 1.0 mg/mg at 2 consecutive measurements at least 7 days apart

 Table 2-1 Definition of notable/extended ranges for key safety laboratory parameters

Novartis	Confidential	Page 29 of 36
SAP Amendment 1		Study No. CICL670F2203

\* If the unit of the parameter (Urinary protein/creatinine ratio) is in mg/mmol then will have to use a conversion factor as 0.00885 to convert into mg/mg unit for further derivation.

For all analyses, creatinine clearance will be re-derived using the Cockcroft-Gault equation described in Section 5.2.1.

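### Responders whose final hold is not followed by a restart leave the general safety tables 30 days after last treatment, with visits still scheduled to Week 104, and the re-initiation tables do not separate AEs before and after restart

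*SAP*

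**What the plan says.** **Window.** SAP 2.1.1 defines "On-treatment period: from day of first administration of study treatment to 30 days after last administration of study treatment". For deferasirox, "The date of last administration of study treatment is defined as the last date when a nonzero actual dose of study treatment was administered"; for phlebotomy it is the last non-zero volume removed. Protocol 10.5.3.1 sets the same limit, "to 30 days after the last dose of study medication or last phlebotomy".

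**Holds.** On reaching SF ≤ 100 µg/L, "deferasirox FCT must be interrupted and the patient enters the maintenance phase" (Protocol 6.1.1). Phlebotomy is also interrupted at that level. Protocol 4.1 permits, but does not require, a restart: at SF ≥ 300 µg/L for deferasirox and above 100 µg/L for phlebotomy. Follow-up goes on: "Patient visits will occur bi-weekly for the first 4 weeks, then every 4 weeks from Week 4 until 104 (EOT") (Protocol 7.1.4).

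**Tables tied to the window.**
- AEs: SAP 2.6.3 counts on-treatment events only.
- AESI: "number and percentage of subjects with at least one event of the AESI occurring during on treatment period will be summarized" (SAP 2.6.5).
- Laboratory: "The summaries will include all assessments available for the lab parameter collected no later than 30 days after the last study treatment administration date" (SAP 2.6.7). Table 5-3 applies the same 30-day limit to the end-of-treatment (EOT) laboratory visit.
- Vital signs: SAP 2.6.8 summarizes on-treatment values only.

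**Not tied to it.** Ocular AEs are repeated for the on- plus post-treatment period (SAP 2.5.2), ocular examinations cover that period (SAP 2.6.2 and 5.3.2), and all deaths are tabulated (SAP 2.6.4). Later data are listed and flagged.

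**Re-initiators.** SAP 2.6.3 repeats most of the AE summaries for patients who held at SF ≤ 100 µg/L and restarted at ≥ 300 µg/L. It gives listings only if fewer than 10 qualify.

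**The concern.** In most trials, last dose plus 30 days closes the window at about the time the patient leaves treatment. Here the primary endpoint itself triggers the hold, so success can end tabulated safety follow-up long before scheduled follow-up ends. Zero-dose days do not extend the window, and the SAP has no rule that keeps a per-protocol hold on-treatment.

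The patient remains in the denominator, because SAP 2.1 bases percentages on all patients in the arm. A crude incidence thus treats the untabulated time as event-free. Protocol 10.5.3 sets the objective as "Safety and tolerability between deferasirox FCT and phlebotomy during 24 months of study period will be assessed", yet outside the ocular and all-deaths summaries no table covers 24 months for these responders. Counted time may also differ between arms, and no exposure-adjusted rate is planned.

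The re-initiation tables raise a related problem. They repeat the whole on-treatment summary in a selected subgroup, so an AE in Week 3, before any hold, counts the same as one after restart. The tables alone cannot show how re-initiation was tolerated.

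**Working it through.** **The plan's own end point.** SAP Table 5-4 puts Week 104 at Study Day 722. The Table 5-3 formula with k = 25 gives (4 + 4×25 − 1)×7 + 1 = 722, which agrees. The window therefore closes early when the last administration falls before Day 722 − 30 = 692. A hold from Week 100 (Day 694) loses nothing. One from Week 96 (Day 666) closes on Day 696 and loses 26 days and the Week 104 visit.

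**Days and visits outside the tables.** Assume the last dose or blood removal is at the hold visit and there is no restart. Days lost = 104×7 − (7 × hold week + 30). Scheduled post-baseline laboratory and vital-sign visits (Protocol Table 7-1) are Week 2 plus Weeks 4, 8, …, 104: 1 + 26 = 27.

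| Final hold | Days lost of 728 | Visits lost of 27 |
|---|---|---|
| Week 24 | 728 − 198 = 530 (73%) | Weeks 32–104: 19 |
| Week 52 | 728 − 394 = 334 (46%) | Weeks 60–104: 12 |
| Week 76 | 728 − 562 = 166 (23%) | Weeks 84–104: 6 |

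The SAP's day numbering gives the same days lost (for example 722 − 192 = 530). None of this needs an event rate. A hold followed by a restart stays inside, because the window runs without gaps from first to last administration.

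**Phlebotomy is exposed too.** Protocol 2.5 cites maintenance every two to four months. With the SAP's 30.4375-day month, a last procedure one full interval before Week 104 leaves 2×30.4375 − 30 = 31 to 4×30.4375 − 30 = 92 days outside.

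**Can a between-arm effect be stated?** Assume the same true rate in both arms (10 per 100 patient-years), no dropout, and responders' holds spread evenly over Weeks 24–76.
- True 24-month incidence: 1 − exp(−0.10×728/365.25) = 18.1%.
- Responder with no restart: the exponent 0.10×(7h + 30)/365.25 runs evenly from 0.0542 to 0.1539, so counted incidence = 1 − (e^−0.0542 − e^−0.1539)/(0.1539 − 0.0542) = 9.8%.
- Arm with 60% responders, none restarting: 0.4×18.1 + 0.6×9.8 = 13.1%.
- Arm with 90% responders, none restarting: 0.1×18.1 + 0.9×9.8 = 10.7%.
- Arm with 60% responders, all on maintenance phlebotomy every 60–120 days to Week 104: 17.6% in responders, so 0.4×18.1 + 0.6×17.6 = 17.8%.

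Deferasirox against phlebotomy could then read 13.1% against 17.8%, 13.1% against 13.1%, or 13.1% against 10.7%, all from equal true rates. The documents do not say which case applies.

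**The case against.** **The window is a pre-specified choice.** Protocol 10.5.3 refers to its own subsections for how safety is assessed, and 10.5.3.1–10.5.3.2 set this window. That stands. A reader might infer that the SAP contradicts the 24-month objective; it does not, because the protocol itself implements the objective this way.

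**The main safety question is covered.** The post-marketing requirement concerns ocular safety, and the ocular summaries span the overall period. That stands too; what remains is general AEs, laboratory data and vital signs in descriptive analyses.

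**Unequal counted time need not favour deferasirox.** A reader might infer from the higher deferasirox restart threshold that its crude AE rates will look too low. The 13.1% against 17.8% case requires that no deferasirox responder restarts while every phlebotomy responder continues to Week 104. Restart is optional in both arms, phlebotomy frequency is left to the physician, and restarted deferasirox is itself interrupted again at SF ≤ 100 µg/L. The documents give no response timing, re-accumulation rate or restart rate. Sampling error is also large: exact 95% intervals are 7.1–21.2% for 13/100 and 8.6–31.4% for 9/50.

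**AE data during holds may be incomplete.** Protocol Table 7-1 and 8.1.1 tie collection to 30 days after last dose, and 8.2.2 ties SAE reporting to 30 days after treatment stops, while 7.2.2 says AEs are collected at every visit. This limits any longer AE table. It does not touch laboratory and vital-sign data, which are scheduled to Week 104.

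**The re-initiation tables meet the endpoint as worded.** Neither document promises a split at restart, and the AE and dosing listings would allow one by hand. That is correct, but the planned tables still mix events from before the hold with events after restart.

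**Conclusion.** The point holds as a gap in the planned tables, not as an error in the window or a conflict between documents. For a responder whose final hold begins more than 30 days before Week 104 without a restart, general safety tables omit up to 530 of 728 days and 19 of 27 visits in the cases worked (final hold at Week 24), falling to 166 days and 6 visits for a final hold at Week 76. These figures assume the patient stays on scheduled visits to Week 104 and that the last dose or procedure coincides with the hold visit.

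How many patients are affected cannot be computed from the documents. A between-arm difference in either direction, or none, is compatible with them, so no claim of bias for or against either arm is supported. The re-initiation tables satisfy their endpoint but do not isolate AEs after restart. This is a worthwhile, inexpensive improvement that uses data already scheduled.

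**What to change.** 1. Keep last administration plus 30 days as the main window.
2. Add laboratory and vital-sign summaries for both arms through the disposition-page EOT date plus 30 days, labelled supplementary. SAP 5.3.2 already anchors ocular EOT on that date.
3. Show time at risk, or exposure-adjusted incidence, beside crude AE percentages, noting that adjustment assumes a roughly constant rate. If the true rate were 20 per 100 patient-years for 26 weeks and 6.67 thereafter in both arms, with 60% responders, no deferasirox restart and maintenance phlebotomy as above, adjusted rates would be 11.6 against 10.3 despite equal true rates.
4. Establish whether AEs were collected during holds. If so, add AE, SAE and AESI summaries for the longer window; if not, state the limit beside the tables.
5. For re-initiators, tabulate AEs with onset on or after the first re-initiation date separately from earlier AEs. If fewer than 10 qualify, mark the split in the listing.

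**Cost.** A few tables and some SAP wording; no new data and no change to any clinical rule. The longer window adds off-drug time that can dilute rates of drug-caused events. With 60% responders, a mean hold at Week 50 (Day 350) and no restart, the added share is 0.6×(728 − 350)/(728 + 30) = 30% of deferasirox time. It must therefore stay supplementary and labelled.
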